#### **4. Study Aims and Objective**

##### **a. Research hypothesis**

In patients that are hypoxic secondary to COVID19, the use of prone positioning will result in a reduction in requirement for invasive mechanical ventilation. Key secondary hypothesis include that prone positioning will result reduced requirement for assisted ventilation, in improved oxygenation as measured by either S/F or P/F ratio, reduced work of breathing.

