###### **Secondary objective**

To assess the effect of prone positioning on:

- Length of time tolerating prone positions measured in minutes from prone to request to return to supine position or emergency repositioning if required
- SpO2: FiO2 ratio (as a surrogate marker of P/F ratio) measured before proning and 1 hours after proning or P/F ratio where arterial line available
- Number requiring increase in ventilatory assistance (CPAP+BIPAP+IMV etc)
- Work of breathing assessment

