## 6. **Study outcome measure**

### a. **Primary outcome measure**

Requirement for invasive mechanical ventilation or death by 28 days post enrolment

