#### ***d. Allocation and Randomisation***

Within 6 hr of fulfilling inclusion criteria, a patient will be randomly allocated either to the prone positioning group or the control group (HFNC alone with no prone positioning therapy). Patients will be randomly allocated to either arm of the study at a ratio based on a 1:1 basis using a REDCAP randomisation process. Randomization will be stratified by site using tables of random permutations using the RECAP database for randomization. The random block length is 4, and random numbers are generated by computer.

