### ***11. Statistical Considerations***

#### ***a. Sample size***

From ICNARC data on patients admitted to ICU with COVID19, 60% required advanced respiratory support. From this, we propose a 60% intubation rate in this cohort as defined above and that proning will decrease it to 40%. From this, 97 patients per group for a beta of 0.2 and alpha 0.05, requiring the need to recruit 196 patients. Interim analysis of data will be conducted using aggregated data as part of the Awake Prone Positioning in COVID Meta-Trial.

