#### ***b. Analysis population***

Data will be analysed on an intention to treat basis with all data for patients who consented to be involved included in baseline data analysis. Outcome data will be analysed for all patients who were positioned in the prone position for any length of time. A further per protocol analysis will be carried out on all patients who tolerated at least 1 hour of the daytime proning time and at least 2 hours of the night time proning period in any 24 hour period. Patients who were rescue prone will be considered a protocol deviation and will be studied as a group. Definition of the two groups: The

patients who receive the prone positioning are classified as prone positioning group. The patients who receive HFNC alone are classified as HFNC group. Comparisons between the two groups: Quantitative continuous variables are given as either means ( $\pm$ SDs) or medians (with inter-quartile ranges) are compared using the unpaired Student's t test or the Mann-Whitney test. Qualitative or categorical variables are compared with the chi square test or the Fisher's exact test. ANOVA for paired tests to compare the same variables collected at different time points are used. The cumulative probability of remaining on spontaneous breathing are compared with the Kaplan-Meier estimate of survival and the log-rank test to compare the two groups. Univariate and multivariate analyses of risk factors for PP failure are performed with logistic regression. All analyses are in intention to treat, and the level of significance is set at 0.05.

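### Section 11b sets one 0.05 level but not when the three key secondary hypotheses may be claimed; if all three are null, the chance of at least one nominally significant result is about 8–15%

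*Combined protocol and SAP*

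**What the plan says.** The plan has one primary outcome (section 6a): "Requirement for invasive mechanical ventilation or death by 28 days post enrolment". The sample size in section 11a is built on it with alpha 0.05 and beta 0.2.

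Section 4a adds further research hypotheses: "Key secondary hypothesis include that prone positioning will result reduced requirement for assisted ventilation", and then "in improved oxygenation as measured by either S/F or P/F ratio, reduced work of breathing". That makes three, each stated with a direction.

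Section 11b gives the only decision threshold: "All analyses are in intention to treat, and the level of significance is set at 0.05". The same section also plans a log-rank comparison, a per-protocol analysis, a separate look at rescue-proned patients, and univariate and multivariate regressions for failure of proning. The available text contains no testing order, no condition on the primary result, no multiplicity method and no exploratory label for any of these.

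The list of secondaries is not stable. "Work of breathing assessment" is among the secondary objectives in section 4c but missing from the secondary outcome measures in section 6b. Oxygenation may be either of two ratios.

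**The concern.** A key secondary hypothesis with a bare 0.05 level attached invites a claim. As the text stands, nothing prevents a key secondary with p below 0.05 from being reported as a significant finding when the day-28 composite is not significant.

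This matters more here than in many trials. The study is open label. Oxygenation is measured one hour after proning, and work of breathing is scored by observation. Such measures could move, by chance or through the open design, without any effect on ventilation or death. A null primary with one nominally significant short-term secondary is therefore a realistic result, and the plan should say beforehand how it would be described.

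**Working it through.** **1. Is the 0.05 two-sided?** Section 11a gives 60% against 40%, alpha 0.05, beta 0.2 and 97 per group. The pooled-variance formula without continuity correction is

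n = [z(0.975)·√(2·0.5·0.5) + z(0.80)·√(0.6·0.4 + 0.4·0.6)]² / (0.6 − 0.4)²

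= [1.960·0.7071 + 0.8416·0.6928]² / 0.04 = 1.969² / 0.04 = 96.9, so 97 per group.

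This matches the plan. The total is 194, two below the stated 196. A one-sided test would need 77 per group, so 0.05 is read as two-sided.

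**2. Three key secondaries, each at two-sided 0.05, all three nulls true.**
- If independent: 1 − 0.95³ = 14.3%.
- Upper bound whatever the dependence: 3 × 0.05 = 15%.

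The documents give no correlation between these outcomes, so it is an assumption. With equally correlated normal test statistics, by numerical integration:

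| Assumed correlation | At least one significant, either direction | At least one significant in favour of proning |
|---|---|---|
| 0 | 14.3% | 7.3% |
| 0.3 | 13.6% | 6.8% |
| 0.5 | 12.5% | 6.3% |
| 0.7 | 10.9% | 5.5% |
| 0.9 | 8.4% | 4.2% |

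The single-test figures are 5% and 2.5%. The calculation treats each key secondary as one between-arm test. For oxygenation that is an assumption, because section 6b times the measurement by proning and gives no matching time point for controls.

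**3. How many tests are in the family?**
- Only the two key secondaries that also appear in section 6b (oxygenation and increased ventilatory assistance): 1 − 0.95² = 9.75% if independent, with an upper bound of 10%.
- Both oxygenation ratios tested, making four: 1 − 0.95⁴ = 18.5% if independent.

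**4. A key secondary significant while the primary is not.** With all four nulls true and a common correlation among the four statistics, simulation (2,000,000 draws per value) gives 13.5%, 12.4%, 10.6% and 8.0% at correlations 0, 0.3, 0.5 and 0.7.

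**5. What a rule would do.**
- Requiring a significant primary first: the chance of any false key secondary claim falls to 0.7%, 1.2%, 2.0% and 2.9% at the same four correlations, again with all four nulls true.
- Bonferroni across the three (0.05/3 = 0.0167 each): 1 − (1 − 0.0167)³ = 4.9% if independent, and lower with positive correlation.

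The condition on the primary protects little if proning truly improves the primary, because the gate is then usually open. That is why a method across the three secondaries is needed as well.

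**The case against.** The strongest reply is that the plan has one primary objective and one primary composite, that its type I error is 5% whatever happens to the secondaries, and that unadjusted secondaries are commonly reported as supportive. The plan nowhere promises family-wise control, so 8–15% is not a departure from anything it states. All of this stands, and it limits how serious the point is.

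A reader might infer from section 11b that the plan expressly allows a key secondary to be claimed after a failed primary. It does not say so. The sentence fixes a level and is silent on when it licenses a claim. Nor can it be read literally for every analysis, since the same section plans a per-protocol analysis. The gap is an inference from what is absent.

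A reader might also take 12–15% as the error rate. That range needs all three nulls true, all three tests counted and a correlation below about 0.6. It also counts errors in both directions, whereas the practical worry is a false claim of benefit.

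Finally, final analysis and co-reporting run through the meta-trial (section 10a). Its analysis plan is not among the documents, so a testing rule may or may not exist there. Section 11b nevertheless sets out this trial's own tests and level, and a reader of this plan cannot tell which secondary results would count as claims.

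**Conclusion.** The point holds as a gap that is cheap to close. With three key secondaries and no true effect on any of them, the chance of at least one nominally significant result is about 8–15% over assumed correlations from 0.9 down to 0, including the 15% bound. For false claims of benefit it is about 4–7%, against 2.5% for one test. If the family is the two outcomes listed in section 6b, the two-sided figure is at most about 10%.

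These figures cover chance alone; they do not measure any bias from the open-label design. They do not show that the primary test is inflated or that a stated figure in the plan is wrong, and the documents would not support either reading.

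**What to change.** Replace the last sentence of section 11b with a short paragraph to this effect:

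- The two-sided 0.05 level is the confirmatory level for the primary composite only.
- Key secondary hypotheses may be claimed as significant only if the primary is significant, and then with a multiplicity method across them, for example Holm. Otherwise each is reported as an estimate with a 95% confidence interval and no claim of significance.
- The log-rank, per-protocol, rescue-prone and risk-factor analyses are supportive or exploratory.

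Make sections 4a, 4c and 6b agree on the key secondaries: decide whether work of breathing is one of them, and name one oxygenation measure with a time point that applies to both arms. A fixed testing order is best left out while these definitions are loose. If the meta-trial plan already contains a rule, cite it and bring section 11b into line.

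The cost is one paragraph and an aligned list, with no extra patients, no extra analyses and no loss of power for the primary. The downside is that a secondary cannot be called significant when the primary is not, and that Holm asks more of the secondaries (0.0167 for the smallest of three p-values). Their estimates and intervals are reported either way.

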**c. *Missing data***

Missing data will be completed using last observation carried forward and the percentage of datasets with full or missing data will be reported.

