### ***10. Schedule of assessment***

#### ***a. Data collection and management***

Data will be collected using an electronic case report form hosted in UCD. Details of CRF attached in appendix B. No patient identifiers will leave hospital unit and all data sent to CRF at NUI Galway will be pseudoanonymised. A collaborative data sharing agreement with UCD and NUI Galway has been developed. Aggregated data will be shared with investigators of the Awake Prone Positioning in COVID Meta-Trial for interim analysis and Anonymised data without personal identifying features will be sent for final analysis and co-reporting of outcomes.

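### Last observation carried forward is the only missing-data rule and does not exempt the day-28 primary outcome, so unknown status becomes an observed non-event, with no missing-data sensitivity analysis planned

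*Combined protocol and SAP*

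**What the plan says.** Section 11c is one sentence. The rule is "Missing data will be completed using last observation carried forward", and the only addition is descriptive: "the percentage of datasets with full or missing data will be reported". Repeated measurements, such as the oxygenation ratios, are not separated from single endpoints.

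The primary outcome (section 6a) is "Requirement for invasive mechanical ventilation or death by 28 days post enrolment". Section 11b names no test specifically for it. The general rule there is "Qualitative or categorical variables are compared with the chi square test", with Fisher's exact test as the alternative. The same section plans a time-to-event comparison: "The cumulative probability of remaining on spontaneous breathing are compared with the Kaplan-Meier estimate of survival", with a log-rank test. It gives no censoring rule and does not call this analysis primary or a sensitivity analysis. It also plans a per-protocol analysis, defined by hours of proning tolerated.

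The sample size (section 11a) is "97 patients per group for a beta of 0.2 and alpha 0.05, requiring the need to recruit 196 patients", based on 60% against 40%. No loss to follow-up is assumed.

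**The concern.** Carrying a value forward can be argued over for a repeated oxygenation measurement. For an outcome that can only move from no event to event, it works in one direction. The eligibility criteria (section 7c) admit patients on high-flow nasal cannula and exclude those who need intubation at once, so everyone starts event-free. Events seen before contact is lost are kept. A patient lost before an event can only be filled in as event-free.

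That filled-in value then enters a chi-square or Fisher comparison as if it had been observed. Where some of these patients later had an event, the event rates are understated and so, usually, is the absolute difference. If the understatement differs between arms, the comparison is biased. With no missing-data sensitivity analysis, the report would not show how far the result depends on patients whose outcome nobody saw.

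**Working it through.** **Inputs.** From section 11a: 60% control, 40% prone, alpha 0.05, power 80%, 196 patients, hence 98 per arm at 1:1. The documents give no loss rate, no share of events unseen and no risk after discharge. All such values below are assumptions.

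**The plan's own figure.** The pooled two-proportion formula, two-sided, without continuity correction, gives 96.9, which rounds up to the stated 97 per group. Power is 0.800 with 97 per arm and 0.804 with 98.

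**Worst case: lost patients carry the full risk.** Let w be the share lost and u the share of their events that go unseen. Carrying forward gives observed rate = p × (1 − w × u). With equal loss, u = 1 and 98 per arm:

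| Loss w | Observed rates | Difference | Power, carried forward | Power, complete case |
|---|---|---|---|---|
| 0 | 60.0% vs 40.0% | 20.0 points | 0.804 | 0.804 |
| 2% | 58.8% vs 39.2% | 19.6 points | 0.788 | 0.796 |
| 5% | 57.0% vs 38.0% | 19.0 points | 0.763 | 0.784 |
| 10% | 54.0% vs 36.0% | 18.0 points | 0.720 | 0.761 |

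The complete-case column uses 98 × (1 − w) per arm and takes loss as unrelated to outcome. The rule itself therefore costs about 1, 2 and 4 points of power. The risk ratio is unchanged.

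**Gap after event-free discharge.** Suppose instead that all lost patients were event-free when last seen, with later risk r. Then observed rate = p − w × r.
- With w = 10% and r = 0 the rates are 60% vs 40%.
- With r = 10% they are 0.60 − 0.10 × 0.10 = 59% vs 0.40 − 0.10 × 0.10 = 39%.
- The difference stays at 20 points and power is about 0.80 in both cases.
- Dropping these patients does worse. The complete-case rates are 0.60/0.90 = 66.7% vs 0.40/0.90 = 44.4% (r = 0), or 0.59/0.90 = 65.6% vs 0.39/0.90 = 43.3% (r = 10%). The difference is inflated to 22.2 points.

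**Differences between arms, no true effect, 60% in both.**
- 10% loss in prone and 5% in control, all later events unseen: 0.60 × 0.90 = 54% vs 0.60 × 0.95 = 57%.
- Equal 10% loss, with all later events unseen in prone but half in control: again 54% vs 0.60 × (1 − 0.10 × 0.5) = 57%.
- In both cases the two-sided type I error is 0.071 (0.073 by exact enumeration of the uncorrected chi-square test). Reversing the arms reverses the direction of the bias.
- With equal loss and equal shares unseen, type I error stays at 0.05.

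**What bounds would show.** Suppose 5 are lost per arm and the design rates hold among the 93 seen: 56 vs 37 events.
- Carried forward, 56/98 vs 37/98 gives p = 0.007.
- Counting the lost prone patients as events and the lost controls as event-free, 56/98 vs 42/98 gives p = 0.046.
- With 8 lost per arm (54 vs 36 events), the two values are 0.010 and 0.153.

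**The case against.** The strongest reply is that little will be missing. Section 9c has reasons for intubation recorded and section 13f covers the hospital course, so in-hospital events are probably captured. The likelier gap is status after discharge, when patients have left hospital event-free and may have little remaining risk. Carrying forward then costs almost nothing, and complete-case analysis would be worse. Censoring at discharge would also be informative, because it gives discharged patients the risk of those still in hospital. This stands. It limits the size of the problem and narrows the remedy, but it does not make an unseen value an observed one.

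A second reply is that section 11b already contains a remedy. The Kaplan-Meier analysis could censor lost patients, but no censoring rule is given and its endpoint is worded as remaining on spontaneous breathing. A reader might also infer that no sensitivity analysis of any kind is planned. That is too strong, since there is a per-protocol analysis, but it addresses adherence and not missing outcomes.

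A reader might further infer that the withdrawal criteria (section 9a), which include not tolerating the prone position, remove prone patients from follow-up and so favour that arm. The documents do not support this. The criteria sit in the intervention section, do not say that follow-up ends, and also cover intolerance of the nasal cannula. Section 11b says "Outcome data will be analysed for all patients who were positioned in the prone position for any length of time", which suggests that stopping early does not remove a patient from analysis.

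Finally, some relevant material cannot be seen. Section 10a says "Details of CRF attached in appendix B", and that appendix is not in the documents. Nor are the rules of the meta-trial to which data go for final analysis. Day-28 status may already be a required field.

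**Conclusion.** The point holds in a limited form. The plan states a rule that, applied as written to the primary outcome, puts a non-event in place of an unknown status, and it plans nothing to test the consequence. That a lost patient counts as a success is the literal result of the rule; the plan does not say so itself.

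The size is unknown. It runs from close to nil (equal loss after event-free discharge, assumed later risk 0 to 10%) to a power of 0.763 at 5% loss and 0.720 at 10% (full design risk, every later event unseen). The second is a worst case and should not be read as the expected loss of power.

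Bias in either direction is possible if the loss, or the share of events unseen, differs between arms. In the example worked here the type I error is about 0.07. Nothing in the documents shows such a difference, so a claim that the rule favours proning would go beyond the text. The wording still merits correction, because the remedy is cheap and the endpoint is primary.

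**What to change.** - In section 11c, remove last observation carried forward for the primary outcome.
- State that ventilation and vital status at day 28 is obtained for every randomised patient, including after discharge and after proning stops, unless consent to data use is withdrawn. The withdrawal criteria themselves need no change for this.
- For status that is still missing, use multiple imputation by arm, conditioning on discharge status and last respiratory support. Do not use complete cases or censoring at discharge.
- Add best- and worst-case bounds as the missing-data sensitivity analysis.
- Report the percentage missing, already promised, by arm.

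The cost is protocol and SAP wording, slightly more analysis work, and a day-28 status check that the endpoint already implies. The study end date (sections 5b and 5c), the choice of primary analysis and the recruitment margin are separate points and are not settled by this change.

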**12. *Data monitoring***

**a. *Data access and Monitoring arrangement***

The eCRF has an audit trail in place, participating centres only have accounts available for delegated people and specific login accounts are created to only edit for their own site. External monitors can only view data and enter queries, they cannot change data. No directly identifiable data will be stored in the eCRF, e.g. only year of birth and no date of birth will be captured. Audit trail in place (eCRF) compliant with 21 CFR part 11. The database is compliant with the EU Directive on data protection 95/46/EC. eCRF only accessible via site-specific (password-regulated) delegated log-in. (21 CFR part 11 compliance). Also compliant with the EU Directive on data protection 95/46/EC. A Standard contractual clauses for the transfer of personal data from the Community to third countries (controller to controller transfers) has been signed

**13. *Regulation, Ethics and Governance***

**a. *Regulatory and ethics approval***

Study has been approved by Galway University Hospitals Research ethics committee and the National research ethics committee (CA2352, 20-NREC-COV-054).

**b. *Protocol compliance***

A Request for sponsorship from the CRFG at NUI Galway has been sought which will provide the necessary manpower for trial oversight, quality, statistical analysis. Online training on study protocol will be conducted prior to site initiation. Investigators will be available for any data entry queries or clinical concerns.

**c. *Good clinical practice***

All individuals who will participate in conducting this study and have signed a delegation log will require an up to date certificate of good clinical practice.

**d. *Indemnity***

Patients will be covered under the HSE Clinical Indemnity Scheme and by indemnity provided by the National University of Ireland, Galway

#### ***e. Patient confidentiality***

A Data privacy impact assessment has been filed for the study. Patient confidentiality will be maintained by keeping data collected in the study coded. The key will be at the local study site where patient is included. No Personal details or identifying data will be transferred from the site to the sponsor where the data will be analysed. The coded data will be securely entered via the electronic case report form which will be managed by NUI Galway. The need data controlled will be the principal investigator, associate investigators, biostatisticians affiliated with NUI Galway. The site lead will have received training in regard to the requirements under GDPR that relate to health research. A data protection impact assessment has been completed and submitted to the SAOLTA data protection officer.

